10.4 Endometrial Safety

For subjects with intact uterus, summary tables of endometrial histology and endometrial thickness will be presented at baseline, Week 12 for each treatment group. Change from baseline to Week 12 in endometrial thickness will be summarized for each treatment group.

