- l May be omitted in subjects with a normal mammogram within 9 months prior to screening for which the results are available.
- m To be assessed based on pill count. When there is a discrepancy between the pill count and the subject-reported compliance, the subject-reported compliance should be used.
- n Do not perform if discontinuation (early termination) occurs PRIOR to VISIT 5 (Week 12).
- o Repeat after cure of infection at V1.

- p Repeat after cure of infection at V2.
- q Follow-up call should occur ON Day 14 after last dose. In case subject does not respond, three follow-up attempts should be made.

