7.6.4 Transvaginal Ultrasound (for Subjects with an Intact Uterus Only)

A transvaginal ultrasound (TVU) will be conducted to assess the uterus and adnexa. Images obtained will also be used to determine endometrial thickness at the central ultrasound laboratory. Date of the TVU will be entered in the eCRF. The TVU must be performed by a trained study staff member and images must be sent to a central reader. The results of the TVU at Visit 1 (Screening), including centrally-determined endometrial

thickness, will be used to assess eligibility. The subject should not be randomized until the centrally read TVU result indicates the endometrial thickness (double-layer) is <4 mm.

If at Screening, the locally read endometrial thickness is evidently, according to the Investigators judgment, more than 4 mm, the subject would not be eligible for the study and the images from the TVU should not be sent to the central ultrasound laboratory.

At 12 weeks (Visit 5), the TVU will be performed and the endometrial thickness (double-layer) will be determined by a central reader following the same procedure. If the subject leaves the study before Week 12, the TVU should be performed as part of the early termination visit.

Any symptomatic and/or large fibroids (estimated size >3 cm) or uterine polyps observed in the TVU at Screening (Visit 1) will exclude the subject from the study. Subjects with endometrial polyps identified during the study period will be discontinued, endometrial polyps should be reported as an AE, and the AE should be captured as the reason for discontinuation.

Detailed procedures will be specified in a separate document. Details about the central ultrasound laboratory are provided in Section 10.1.

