Assessment of biopsies will be made according to predefined and generally accepted microscopic criteria (Blaustein's classification). Subjects found to have endometrial hyperplasia or endometrial cancer at screening will be excluded from the study. Subjects found to have endometrial hyperplasia or endometrial cancer during the study will be discontinued and endometrial hyperplasia or endometrial cancer should be reported as an AE, and the AE should be captured as the reason for discontinuation. The subject will be referred for standard of care clinical management and followed to complete resolution (reports of any medical or surgical procedures and the resultant pathology must be provided to the Sponsor). The interpretation of the results by the three pathologists and their agreement or disagreement will be managed as described above in order to determine the final diagnosis for all endometrial biopsies (those scheduled during the study and "for cause" [for example, vaginal bleeding]).

The date of specimen collection will be entered in the eCRF. Details about the central pathology laboratory are provided in Section 10.1.

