9. PLANNED STATISTICAL METHODS

9.1 General Considerations

The statistical analysis will be performed by the Sponsor or designee. Detailed statistical analysis methods will be specified in a statistical analysis plan (SAP) according to this section of the study protocol. Analyses deviating from those outlined in the protocol will be clearly specified in the SAP, and the reason for deviation from the protocol will be described. The SAP will be finalized before breaking the study blind.

Unless otherwise noted, continuous variables will be summarized by using the number of non-missing observations, arithmetic mean, standard deviation (SD), median, minimum, and maximum values as descriptive statistics; categorical variables will be summarized by using the frequency count and the percentage of subjects in each category as descriptive statistics.

All statistical tests will be performed at the 0.05 significance level using two-sided tests, except where otherwise noted.

All subject study data, including data not appearing in tables, will be presented by-subject data listings. In general, all tables will be presented by treatment group. Individual subject data and any derived data will be presented by treatment and subject. All analyses and tabulations will be performed by using SAS® Version 9.2 or higher.

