9.11.4 Endometrial Safety

Summary statistics for endometrial thickness and endometrial histology will be presented for each scheduled time point measured after randomization and for the change from baseline to each time point. Baseline will be the last value obtained before initial dose.

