3.2 Secondary Objectives

Objective 1: To assess the effect of ospemifene 60 mg relative to placebo in change from baseline to Week 12 on:

- Severity of other VVA symptoms different from vaginal dryness (i.e., dyspareunia, vulvar/vaginal itching/irritation, dysuria [difficult/painful urination], vaginal bleeding associated with intercourse)
- Markers of bone metabolism
- Vaginal Health Index (VHI)
- Vulvar Health Index (VuHI)

Objective 2: To assess the effect of ospemifene 60 mg relative to placebo in change from baseline to Week 12 on:

- Female Sexual Function Index (FSFI)
- Urinary Distress Inventory (UDI-6)

Objective 3: To assess the effect of ospemifene 60 mg QD, relative to placebo, over 12 weeks on endometrial histology

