6.3 Study Day and Analysis Windows

Day 1 is the initial dose date for subjects. Previous day to Day 1 is expressed as Day -1, and days before Day -1 in Screening Period are expressed as Day -2, Day -3, ... , etc.

Allowance window for each of the scheduled visits is shown in Table 1.

Allowance window for diary data is shown in Table 2.

If more than one visit occurs during a visit window, the one closest to the target day will be assigned to the visit. If two visits are equidistant from the target day, the latter visit will be assigned to the visit for post-baseline values.

If a subject discontinues from the study, the data obtained at early termination visit will be treated as one visit data based on the allowance windows.

Table 1 Definition of Visit Window

Scheduled Visit	Target Day	Window (Days)
Visit 1	Day -28	≤ Day -1
Visit 2 (Day 1)	Day 1(Randomization)	Day 1
Visit 3 (Week 4)	Day 29	Day 16 to Day 43
Visit 4 (Week 8)	Day 57	Day 44 to Day 71
Visit 5 (Week 12)	Day 85	Day 72 to Day 99
Early termination	Last dosing date	+ 14

Table 2 Definition of Diary Data Window

Week	Daily Data	Weekly Data (Target Day)
Week 1	Day 1 to Day 7	Day 4 to Day 10 (Day 7)
Week 2	Day 8 to Day 14	Day 11 to Day 17 (Day 14)
Week 3	Day 15 to Day 21	Day 18 to Day 24 (Day 21)
Week 4	Day 22 to Day 28	Day 25 to Day 31 (Day 28)
Week 5	Day 29 to Day 35	Day 32 to Day 38 (Day 35)

Week	Daily Data	Weekly Data (Target Day)
Week 6	Day 36 to Day 42	Day 39 to Day 45 (Day 42)
Week 7	Day 43 to Day 49	Day 46 to Day 52 (Day 49)
Week 8	Day 50 to Day 56	Day 53 to Day 59 (Day 56)
Week 9	Day 57 to Day 63	Day 60 to Day 66 (Day 63)
Week 10	Day 64 to Day 70	Day 67 to Day 73 (Day 70)
Week 11	Day 71 to Day 77	Day 74 to Day 80 (Day 77)
Week 12	Day 78 to Day 84	Day 81 to Day 87 (Day 84)

Assessments that occur more than 14 days after the last dose of study medication will be excluded from the above visit windows.

The baseline is defined as the last value that is observed prior to the first dose of study medication. For a variable that is planned to be observed at screening and randomization, the data at randomization will be used as baseline. For such variable, if the data at randomization is missing for a subject, the data observed at screening will be used as baseline.

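### SAP 10.4 tabulates endometrial histology only at baseline and Week 12 (Day 72 to 99), so a for-cause hyperplasia or cancer diagnosis before Day 72 normally never enters the post-baseline histology table.

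*SAP*

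**What the plan says.** - **What is tabulated.** SAP 10.4 restricts the output to women with a uterus and says that "summary tables of endometrial histology and endometrial thickness will be presented at baseline, Week 12 for each treatment group". Change in thickness is summarized from baseline to Week 12 only. Protocol 9.11.4 has the same scope: "Summary statistics for endometrial thickness and endometrial histology will be presented for each scheduled time point measured after randomization".
- **What Week 12 means.** SAP 6.3, Table 1, gives Week 12 a target of Day 85 and a window of Day 72 to Day 99. For a woman who discontinues, "the data obtained at early termination visit will be treated as one visit data based on the allowance windows". Table 1 also has an early-termination row, but 10.4 does not tabulate it.
- **What happens to a diagnosis.** Protocol 7.6.5: "Subjects found to have endometrial hyperplasia or endometrial cancer during the study will be discontinued". The finding is reported as an AE and recorded as the reason for discontinuation. The same section sends for-cause biopsies through the three-pathologist process used for scheduled ones.
- **Biopsy at early termination.** Footnote n to the protocol's Table 3.1-1 reads "Do not perform if discontinuation (early termination) occurs PRIOR to VISIT 5 (Week 12". Protocol 8.5 accordingly lists no biopsy among the early-termination procedures.
- **Ultrasound at early termination.** Protocol 7.6.4: "If the subject leaves the study before Week 12, the TVU should be performed as part of the early termination visit".
- **The objective served.** SAP 3.2: "Objective 3: To assess the effect of ospemifene 60 mg QD, relative to placebo, over 12 weeks on endometrial histology".

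**The concern.** The objective covers the whole 12 weeks, but the only histology table the SAP text describes looks at a window that opens on Day 72. Vaginal bleeding can lead to a biopsy at any time during treatment (protocol 7.6.6). If that biopsy shows hyperplasia or cancer before Day 72, the woman is discontinued and does not reach the scheduled Visit 5 biopsy. She is missing from the table because of the very finding the table exists to show. That is different from ordinary dropout, where the reason for leaving may have nothing to do with the endometrium.

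At stake is whether the report gives a direct 12-week rate of endometrial pathology among the women at risk. A reader of the 10.4 table alone could see no case in an arm where one had been adjudicated.

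A lesser gap concerns thickness. The protocol requires an ultrasound at early termination, yet a result before Day 72 goes into no endometrial summary.

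**Working it through.** **1. The window.** The Table 1 targets for Weeks 8 and 12 are Day 57 and Day 85. Their midpoint is (57 + 85)/2 = 71, so Week 12 opens on Day 72, as the SAP prints. Placing endometrial results by study day gives:

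| Study day of result | Table 1 visit | Tabulated in SAP 10.4? |
|---|---|---|
| 2 to 15 | none | no |
| 16 to 43 | Week 4 | no |
| 44 to 71 | Week 8 | no |
| 72 to 99 | Week 12 | yes |

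No post-baseline result dated before Day 72 can reach the Week 12 column.

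**2. Does Week 12 here silently include early termination?** The schedule column is headed Wk 12/ET, so one might think so. But SAP 9.2.10 analyzes bone markers to Week 12 and, separately, to Week 12/ET, and SAP 10.3 names early termination apart from Week 12. Section 10.4 says Week 12 only, and 6.3 places early-termination data by day.

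**3. The path of one case.** Bleeding before Day 72, then a for-cause biopsy, adjudicated hyperplasia or cancer, discontinuation, and no routine biopsy at early termination. Result: no Week 12 histology.

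**4. Size, by illustration only.** The documents give no rate of dropout, for-cause biopsy or hyperplasia. Assumptions:
- 300 women per arm (SAP 4.3), with the 60% cap on women without a uterus reached (SAP 4.2), so 300 × 0.40 = 120 per arm have a uterus.
- 5% to 20% of these leave before Day 72.
- One leaver has a for-cause hyperplasia diagnosis.
- Every woman who stays has an evaluable Week 12 biopsy.

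Week 12 table n = 120 − leavers. Evaluable post-baseline n = Week 12 n + 1. Limits are exact (Clopper-Pearson) 95%.

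| Leave before Day 72 | Leavers | Week 12 table (upper limit) | Evaluable biopsy | All with a uterus |
|---|---|---|---|---|
| 5% | 6 | 0/114 (3.18%) | 1/115 = 0.87% | 1/120 = 0.83% |
| 10% | 12 | 0/108 (3.36%) | 1/109 = 0.92% | 1/120 = 0.83% |
| 15% | 18 | 0/102 (3.55%) | 1/103 = 0.97% | 1/120 = 0.83% |
| 20% | 24 | 0/96 (3.77%) | 1/97 = 1.03% | 1/120 = 0.83% |

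The exact interval for 1/120 is 0.02% to 4.56%. At the other extreme, with a uterus present in all 300 women per arm, the Week 12 table shows 0/285 to 0/240 against 1/300 = 0.33% (0.01% to 1.84%).

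**5. Thickness.** If each leaver had the required ultrasound, 6 to 24 results per 120 women would go untabulated.

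**The case against.** The strongest reply is that nothing here is an error. Protocol 9.11.4 asks for scheduled time points and SAP 10.4 delivers them. The only scheduled post-baseline biopsy is at Visit 5, laboratory data use the same baseline and Week 12 layout (SAP 10.3, items 1 and 2), and analysis of observed data without imputation is stated policy. This stands. A reader might infer that the SAP departs from the protocol; it does not, and the gap is shared by both documents.

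Second, the safety signal is already reported by arm. Polyps, hyperplasia and cancer must be recorded as AEs. They therefore reach the system organ class/preferred term TEAE table and the table of TEAEs leading to withdrawal, both with a between-arm difference and 95% CI (SAP 10.1). Protocol 9.1 adds that "All subject study data, including data not appearing in tables, will be presented by-subject data listings". This also stands, and it rules out the inference that cases are hidden or lost. What remains is that those tables use the whole Safety Population, including women without a uterus, and listings give no rate. A reader might also assume that the tabulation of reproductive system-related TEAEs fills the gap, but SAP 10.1 does not say which terms belong to it.

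Third, the illustration rests on one inserted case, and the intervals for 0/114 and 1/120 overlap almost entirely. That is fair. The contrast shows how the table behaves, not how often it happens. The illustration also ignores insufficient samples, which protocol 7.6.5 anticipates.

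Fourth, neither alternative denominator gives a clean rate. Counting all women with a uterus treats unbiopsied leavers as having no diagnosis. Counting only those with an evaluable biopsy admits early leavers only when they were biopsied for cause. Both limits are real, which is why the two should be shown together.

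Fifth, Objective 3 names histology, not thickness. This stands, so the thickness table is a secondary supplement only.

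Last, the table shells are in a separate document (SAP 1) that is not available here. They may already contain such a display; the SAP text does not describe one.

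**Conclusion.** The gap is real but limited. On the SAP text, a for-cause diagnosis of hyperplasia or cancer before Day 72 normally removes the woman from the only histology table described for Secondary Objective 3, and the omission depends on the outcome. It is a gap in the summary, not a contradiction between the documents or a loss of events.

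The number of cases affected cannot be derived. It is probably small, because every routine post-baseline biopsy is scheduled at Week 12. The figures of 0/114 to 0/96 against 1/120 = 0.83% hold only under the stated assumptions: the 60% cap reached, 5% to 20% leaving before Day 72, one for-cause case, and complete Week 12 biopsies otherwise. They do not support a claim that the between-arm comparison is biased by any particular amount.

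The primary efficacy analyses are unaffected. The change is worth making because it is cheap and uses conventions already in the SAP: laboratory limits are assessed at any time point (10.3, item 3) and bone markers at Week 12/ET (9.2.10).

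**What to change.** Keep the Week 12 table and add to SAP 10.4:

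1. **Worst post-baseline histology per woman.** Tabulate the most severe centrally adjudicated diagnosis up to Visit 5 or early termination, from scheduled and for-cause biopsies, labelled by indication. Show it over (i) all Safety Population women with an intact uterus and (ii) those with at least one evaluable post-baseline biopsy. Give insufficient and absent samples their own rows. Report a 95% CI for the between-arm difference, consistent with SAP 10 and 13.1. If no case occurs in either arm, report exact per-arm limits, because a Wald interval for the difference then has zero width.
2. **Secondary supplement.** Summarize endometrial thickness and its change from baseline at Week 12/ET beside the Week 12 summary.

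The cost is a few extra tables from data already collected and centrally read, with no new procedure and no change to clinical rules. The downsides should be footnoted. The first table mixes biopsy indications. Its all-women denominator counts unbiopsied leavers as having no diagnosis, and its evaluable-biopsy denominator can overstate the rate. Both supplements mix exposure durations.

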10.5 Other Safety Variables

Summary table of BMI will be presented at baseline, Weeks 4, 8, 12 for each treatment group. Change from baseline to each timepoint will also be summarized by treatment group.

11 INTERIM ANALYSES

No interim analysis is planned in this study.

12 PROGRAMMING CONVENTIONS

Unless otherwise stated, tables, figures, and listings (TFLs) will be made in accordance with the following specifications on programming:

1) Display digit of various statistics

The display digit of various tests (such as laboratory tests) is as specified for each respective test, in principle. Display digit of statistics for efficacy and safety analyses are defined in Table 8.

Table 8 Display Digit of Statistics for Efficacy and Safety

Statistics		Display Digit
Efficacy and Safety	The number of subjects	Displayed as integer
	Mean, median, 95% confidence interval	One more decimal place than raw data
	Standard deviation, standard error	One more decimal place than raw data
	Maximum, minimum	Same number of decimal places as raw data
	Percentage (%)	Round off to one decimal place
	p-value	Round off to four decimal places Note: p < 0.0001 is displayed as “< .0001”
VVA symptoms	Mean, median, 95% confidence interval, standard deviation, standard error	Round off to two decimal place

2) Handling of outliers

Possible outliers will not be omitted from the analyses.

3) Categories used in the summarization

Categories used in the summarization of items are shown in Table 9. The breakdown of categories may be changed with blind inspection of distribution as needed.

Table 9 Subject Characteristics and Items of Therapeutic Process

Items	Categories
Age (years)	< 45, >= 45 to < 55, >=55 to < 65, >= 65
BMI (kg/m ²)	< 18.5, >=18.5 to < 25, >=25 to < 30, >=30
Ethnicity	Not Hispanic or Latino, Hispanic or Latino, Not reported, Unknown
Race	American Indian or Alaska Native, Asian, Black or African American, Native Hawaiian or Other Pacific Islander, White, Other
Uterus	Yes, No
Current hot flushes	Yes, No
Previous hormone treatment	None, any hormone treatment, hormone replacement therapy (excluding vaginal), vaginal hormone products
Number of Days of Treatment Exposure within Week 12 (days)	>=1 to <= 7, >=8 to <= 14, >=15 to <= 28, >=29 to <= 42, >=43 to <= 56, >=57 to <= 70, >=71 to <= 84, >= 85
Number of Days of Treatment Exposure after Week 12 (days)	>=1 to <=14, >=15 to <=28, >=29 to <=56, >=57 to <=84, >=85 to <=168, >=169 to <=273, >=274 to <=364, >=365
Medication compliance (%)	< 85, >= 85

13 CHANGES FROM PROTOCOL

13.1 Safety Analysis

- Calculation of the CI of the incidence proportion for each treatment group was planned using the Clopper-Pearson method in the Section 9.11.1. It was replaced with the CIs for the difference between treatments because these are more informative.

Appendix 1 Schedule of Time and Events

Evaluation	Screening		Randomization		Treatment			FU ^d
	V1	V2	V3	V4	V5	TC		
	Within 4 Weeks Prior to Day 1 ^a	Day 1	Wk 4	Wk 8	Wk 12/ET	Wk 14		
Informed Consent	X							
Assign Subject ID Number ^b	X							
I/E Criteria	X	X						
Demographics	X							
Medical History ^c	X							
Physical Examination	X	X			X			
Electrocardiogram	X							
Breast Examination	X	X			X			
Gynecological Examination	X ^o	X ^p			X			
Safety Laboratory Tests ^d	X	X ^{e,p}			X ^e			
Hormone Levels ^f		X			X			
FSH ^g	X							
Markers of Bone Metabolism ^h		X			X			
Urinalysis	X	X			X			
Urine Dipstick ⁱ	X	X						
Vital Signs (blood pressure, pulse, body temperature)	X	X	X	X	X			
Height	X							
Weight (BMI)	X	X	X	X	X			
Prior Therapy	X	X						
Concomitant Therapy			X	X	X		X	
Adverse Events	X ^j	X	X	X	X		X	

Evaluation	Screening		Randomization		Treatment			FU ^q
	V1	V2	V3	V4	V5	V6	V7	TC
	Within 4 Weeks Prior to Day 1 ^a	Day 1	Wk 4	Wk 8	Wk 12/ ET			Wk 14
Cervical PAP Smear	X ^o							
Vaginal pH	X ^o	X ^p	X	X	X			
Vaginal Smear/ Maturation Index	X ^o	X ^p	X	X	X			
Vaginal Health Index (VHI)		X	X	X	X			
Vulvar Health Index (VuHI)		X	X	X	X			
Vulvo-vaginal Imaging ^k		X			X			
Endometrial Thickness (TVU)	X				X			
Endometrial Histology (Biopsy)	X				X ⁿ			
Mammogram	X ^l							
Dispense eDiary/Return eDiary		X			X			
eDiary Compliance			X	X	X			
Assessment of symptoms of VVA	X ^o	X ^p	X	X	X			
Dispense Study Medication		X	X	X				
Dispense Lubricant		X	X	X				
Study Medication Compliance ^m			X	X	X			
Reinforce Compliance with Study Medication		X	X	X				
Study Medication Return			X	X	X			
Female Sexual Function Index (FSFI)		X	X	X	X			
Urinary Distress Inventory (UDI-6)		X	X	X	X			

ET = early termination; FU = follow-up; TC = telephone call

- a Enough time between Visit 1 and Visit 2 should be allowed to receive the results of tests conducted as part of Visit 1; therefore, Visit 2 should not take place earlier than 1 week after Visit 1.
- b Subject ID number will be assigned through the interactive web or voice response system (IxRS).

- c Medical history should be captured for the 2 years prior to screening, except for any history of cancer which should be captured regardless of the time.
- d Safety laboratory tests: red blood cell (RBC) count, white blood cell (WBC) count, differential, platelet count, hemoglobin (Hgb), hematocrit (HCT), mean corpuscular hemoglobin (MCH), mean corpuscular hemoglobin concentration (MCHC), mean corpuscular volume (MCV), RBC distribution width (RDW), mean platelet volume (MPV), albumin, alanine aminotransferase (ALT), aspartate aminotransferase (AST), total bilirubin, creatinine, estimated glomerular filtration rate (eGFR), total protein, glucose, uric acid, blood urea nitrogen (BUN), creatine kinase (CK), thromboplastin time, fibrinogen, antithrombin III, factor V Leiden (screening only), protein-C, protein-S, lipids total cholesterol, LDL cholesterol (LDL-C), HDL cholesterol (HDL-C) and triglycerides.
- e Subjects should be fasting for at least 8 hours prior to blood sample collection.
- f Hormones: Estradiol (E2), follicle-stimulating hormone (FSH), luteinizing hormone (LH), sex hormone-binding globulin (SHBG), free and total testosterone.
- g FSH values may be measured for confirmation of postmenopausal status (inclusion criterion No. 3) in women ≥ 45 years old who do not remember the date of the last spontaneous menstrual period OR women who have had a hysterectomy WITHOUT oophorectomy.
- h Markers of bone metabolism: Markers of bone resorption: serum N-terminal telopeptide of type 1 collagen (NTX), serum C-terminal telopeptide of type 1 collagen (CTX), serum bone sialoprotein (BSP), urinary deoxypyridinoline (DPD), and serum tartrate-resistant acid phosphatase 5b (TRACP-5b). Markers of bone formation: serum total alkaline phosphatase, serum bone-specific alkaline phosphatase (BSAP), serum N-terminal propeptide of type 1 collagen (PINP), and serum osteocalcin.
- i At Visits 1 and 2, in addition to obtaining a sample for urinalysis, a urine dipstick will be used to rule out urinary tract infections prior to randomization. Subjects otherwise eligible, who are found to have a urinary tract infection should receive treatment and may continue after confirmation of cure.
- j Adverse events spontaneously reported after signature of the informed consent should be captured.
- k Unless subject withdraws consent for vaginal imaging during the course of the study, if the quality of the photographs is not adequate as assessed by Canfield, a re-shoot should be scheduled as soon as possible but no more than seven days after the original shoot day.
- l May be omitted in subjects with a normal mammogram within 9 months prior to screening for which the results are available.
- m To be assessed based on pill count. When there is a discrepancy between the pill count and the subject-reported compliance, the subject-reported compliance should be used.
- n Do not perform if discontinuation (early termination) occurs PRIOR to VISIT 5 (Week 12).
- o Repeat after cure of infection at V1.
- p Repeat after cure of infection at V2.
- q Follow-up call should occur ON Day 14 after last dose. In case subject does not respond, three follow-up attempts should be made.

